5.0 Dosing Delays/Dose Modifications

Patients experiencing unacceptable toxicity directly attributable to the study drugs should temporarily stop treatment according to the guidelines in the dose adjustment schema.

Toxicity grading will be according to the NCI CTCAE, v4. To prevent unnecessary morbidity, the following guidelines for dose adjustment for drug-related toxicities are recommended.

Dose Reductions for non-hematologic toxicity possibly related to study drugs should be performed according to the following table:

Toxicity	Grade	Actions
Non-hematological (excludes myalgia/arthralgia responding to treatment, inadequately treated vomiting and diarrhea, or electrolyte abnormalities unless not responding to optimal supplementation)	3 or 4	Hold therapy until recovery to Grade ≤ 1 , then re-start and reduce one dose level unless approved by PI on case to case basis. If toxicity recurs again, hold therapy until recovery to grade ≤ 1 , then re-start and reduce one dose level. Dose reductions below dose level -2 will be considered on an individual basis after discussion with the PI. For grade 4, the recommendation is to discontinue Sorafenib
Non-hematological (excludes myalgia/arthralgia responding to treatment, inadequately treated vomiting and diarrhea, or electrolyte abnormalities unless not responding to optimal supplementation)	Persistent 2-considered clinically significant or upon patient's request	Hold therapy until recovery to Grade ≤ 1 , then re-start and reduce one dose level unless approved by PI on case to case basis. If toxicity recurs again, hold therapy until recovery to grade ≤ 1 , then re-start and reduce one dose level. Dose reductions below dose level -2 will be considered on an individual basis after discussion with the PI.

Patients in whom the toxicity occurs or persists beyond the planned completion of drug administration for the cycle will have the dose reductions implemented in subsequent cycles provided the toxicity has resolved as specified in the table above.

5.1 Myelosuppression:

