- Patient has not experienced hematologic grade 4 toxicity believed to be treatment related, and
- This has been discussed and approved by the PI and recorded in the patient's clinical records

Dose reductions/modifications/delays:

Dose reductions for sorafenib-specific non hematologic toxicity during subsequent cycles should be performed according to the table in section 5.3 above. Dose modification suggestions for specific toxicities can be found below.

Dose reduction to 200 mg twice daily, 200 mg once daily, and then 200 mg every other day will be allowed depending on the type and severity of toxicity encountered, provided that criteria for patient withdrawal from study treatment have not been met. The following tables describe the recommended dose modifications for sorafenib-associated toxicities:

Variation in the dosing schedules discussed may be allowed if thought to be in the best interest of the patient and after discussing with the study PI.

Suggested dose levels for each drug (adjustments to the dose of each drug can be done independently of the other):

Dose level	Sorafenib	Dose level	Azacytidine
-2	200 mg po daily	-2	50 mg/m ² SC/IV daily x 3
-1	200 mg po bid	-1	50 mg/m ² SC/IV daily x 5
0	400 mg po bid	0	75 mg/m ² SC/IV daily x 7
+1	600 mg po bid	+1	None

Proposed Dose modification for Sorafenib Associated toxicity

Table 1: Suggested Dose Modifications for Sorafenib for Hand-Foot Skin Reaction

Skin Toxicity Grade	Occurrence	Suggested Dose Modification
Grade 1 Numbness, dysesthesia, paresthesia, tingling, painless swelling, erythema or discomfort of the hands or feet which does not disrupt the patient's normal activities	Any Occurrence	Continue treatment with Sorafenib and consider topical treatment for symptomatic relief.
Grade 2 Painful erythema and swelling of the hands or feet and/or discomfort affecting the patient's normal activities	1 st Occurrence	Continue treatment with Sorafenib and consider topical treatment for symptomatic relief. If no improvement within 7 days see below
	No improvement within 7 days or 2 nd or 3 rd occurrence	Interrupt Sorafenib until toxicity resolves to Grade 0-1. When resuming treatment, decrease by 1 dose level
	4 th occurrence	Discontinue Sorafenib treatment

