Grade 3 Moist desquamation, ulceration, blistering or severe pain of the hands or feet, or severe discomfort that causes the patient to be unable to work or perform activities of daily living	1 st or 2 nd occurrence	Interrupt Sorafenib treatment until toxicity resolves to Grade 0-1. When resuming treatment decrease Sorafenib by 1 dose level
	3 rd Occurrence	Discontinue Sorafenib treatment

At first occurrence of HFSR, independent of grade, prompt institution of supportive measures such as topical emollients, low potency steroids, or urea-containing creams should be administered.

Table 2: Dose Modifications for Sorafenib-Associated Toxicity¹

Toxicity	Grade 1	Grade 2	Grade 3*	Grade 4*
Non-hematologic	Continue at the same dose level.	Reduce and Continue at the same dose level.	Withhold ^b dose until toxicity is grade ≤ 1 , then resume treatment decreasing by 1 dose level. If patient experiences a second grade 3 toxicity, withhold ^b dose until toxicity is grade ≤ 1 , then reduce dose by an additional dose level	Discontinue protocol therapy
a. Also excludes nausea/vomiting that has not been pre-medicated, and diarrhea b: If no recovery after 60 day interruption, treatment should be discontinued unless subject is deriving clinical benefit c: If more than 2 dose reductions are required, treatment should be discontinued.				
Toxicity	Grade 1	Grade 2	Grade 3*	Grade 4*
Hematologic	Continue at the same dose level.	Continue at the same dose level.	Withhold dose until toxicity is grade ≤ 2 , then resume treatment decreasing by 1 dose level ^b . If patient experiences a second grade 3 toxicity, withhold dose until toxicity is grade ≤ 2 , then reduce dose by an additional dose level	Withhold ^a dose until toxicity is grade ≤ 2 , then reduce dose by 2 dose levels ^b and resume treatment, or discontinue at the discretion of the principal investigator after discussion with study supporter.

a. If no recovery after 28 day delay, treatment should be discontinued

b. If more than 2 dose reductions are required, treatment should be discontinued.

Hypertension:

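### The general sorafenib dose-modification text needs reconciling: one grade 2 cell cannot be followed, the reduction limits disagree, the grade 4 scope is unclear, and one cross-reference fails

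*Combined protocol and SAP*

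**What the plan says.** Two general tables deal with non-hematologic toxicity that may be due to sorafenib: the table in section 5.0, and Table 2 in section 5.2.

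- **Grade 2.** Table 2 says "Reduce and Continue at the same dose level". The section 5.0 row is limited to "Persistent 2-considered clinically significant" events or those where the patient asks for a change. Its action is to hold until recovery, "then re-start and reduce one dose level unless approved by PI on case to case basis".
- **Grade 4.** Section 5.0 puts grades 3 and 4 in one hold, restart and reduce row, and closes that row with "For grade 4, the recommendation is to discontinue Sorafenib". Table 2 says "Discontinue protocol therapy". The heading of the dose-level table says that "adjustments to the dose of each drug can be done independently of the other".
- **Reduction limit.** The section 5.2 text permits 200 mg twice daily, then once daily, then every other day, according to the kind and severity of toxicity and provided withdrawal criteria are not met. The dose-level table ends at -2 (200 mg daily). Section 5.0 leaves doses below -2 to case-by-case discussion with the PI. A footnote to each part of Table 2 reads "If more than 2 dose reductions are required, treatment should be discontinued", and a footnote to Table 3 (hypertension) takes patients off protocol therapy beyond two reductions.
- **Cross-reference.** Section 5.2 sends sorafenib-specific non-hematologic reductions to a table in section 5.3 above.

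**The concern.** These are the instructions a treating physician consults when a patient has a drug-related toxicity. If the text gives two actions for one event, or one action that cannot be performed, sites may manage the same event differently. A deviation is also hard to identify when the rule deviated from is not settled. What is at stake is the safe and uniform handling of toxicity.

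**Working it through.** No plan figure needs reproducing and no statistical formula applies. The check sets the passages side by side and counts reduction steps.

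**1. Grade 2 non-hematologic.** A dose cannot be both reduced and kept at the same level. In Table 2, the non-hematologic grade 1 cell and the hematologic grade 2 cell each give only the instruction to continue. That raises the possibility that a deletion mark was lost, which only the source file can show. Section 5.0 does not fill the gap, because its grade 2 row covers only persistent, clinically significant or patient-requested events. Hand-foot skin reaction and hypertension have their own Tables 1 and 3. Every other grade 2 non-hematologic event has only the Table 2 cell.

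**2. Reduction limit.** The inputs are the section 5.2 ladder and the dose-level table. Level 0 is 2 x 400 = 800 mg/day.

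| Reduction from level 0 | Section 5.2 text | Mean mg/day | Share of level 0 | Dose-level table | Table 2 limit (single-level reductions) |
|---|---|---|---|---|---|
| 1st | 200 mg twice daily | 2 x 200 = 400 | 400/800 = 50% | -1 | within |
| 2nd | 200 mg once daily | 200 | 200/800 = 25% | -2 | within |
| 3rd | 200 mg every other day | 200/2 = 100 | 100/800 = 12.5% | none | exceeded |

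At the third row section 5.2 allows continuation at a lower dose, section 5.0 allows it to be considered with the PI, and the Table 2 footnote ends treatment.

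This result depends on how reductions are counted. The limit is worded in reductions, while the hematologic grade 4 cell of Table 2 says "reduce dose by 2 dose levels" in one action. There are two ways to count from level 0:

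- If a two-level drop is one reduction, then 0 to -2 is the first and -2 to the third step is the second. Two is not more than two, so the third step can be reached.
- If it is two reductions, the third step is the third reduction and treatment ends.

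The documents do not say which count applies.

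The proviso on withdrawal criteria does not resolve this. Section 4.3 lists 4 criteria and section 10.0 lists 5, and none mentions a number of reductions. If the proviso is instead read as taking in the Table 2 footnotes, it rules out the third step whenever that step is reached by single-level reductions from level 0, which is the order in which the ladder sets out its steps.

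In the non-hematologic part of Table 2 the marker for this footnote (c) is not visible in the text as read, which may be an extraction loss. The same limit is anchored in the hematologic part (footnote b), and the section 5.2 ladder is not confined to one type of toxicity.

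**3. Grade 4 non-hematologic.** Both tables point to stopping sorafenib. Two differences remain. The first is force: section 5.0 makes a recommendation inside a row that also provides for restart, and Table 2 gives a plain instruction with no restart. The second is scope: section 5.0 names sorafenib, and Table 2 names protocol therapy, which is not defined. Because the two drugs may be adjusted separately, stopping one does not imply stopping the other, and the status of azacitidine is unclear.

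**4. Cross-reference.** The numbered headings in section 5 are 5.0, 5.1 and 5.2. The only general non-hematologic table above the reference is the one in section 5.0, so that is the likely target.

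**The case against.** The strongest reply has four parts.

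**The guidance is advisory.** Tables are called suggested, proposed or recommended, and variation is allowed with the PI. This is true and limits the practical effect. But permission to depart from a rule does not say what the rule is.

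**Some order is signalled.** Section 5.2 first directs sorafenib-specific non-hematologic reductions to the table above and then introduces suggestions for specific toxicities below. This has some weight. However, Table 2 is general rather than toxicity-specific, section 5.0 also describes its guidelines as recommended, and no sentence says which prevails. Even if section 5.0 governs, it is silent on other grade 2 events, and it is more permissive on the reduction limit than the footnotes.

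**The limits can be partly harmonised.** A two-level drop may count as one reduction, and Table 1 provides for decreases at more than one recurrence of grade 2 hand-foot reaction before discontinuation. The first point stands and confines the certain conflict to successive single-level reductions. The second concerns a toxicity-specific table and could be a stated exception, but the text does not present it as one.

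**Weight.** Section 2.1 reports that no grade 4 toxicities were seen in single-agent phase I studies of sorafenib, and few of grade 3 or 4 in the later trial. Those data suggest some of these situations may be uncommon, but they do not describe this combination or this population.

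A reader might infer that the two tables order opposite actions at grade 4, that a third reduction is always barred by Table 2, or that the inconsistencies disturb evaluability for efficacy or the toxicity monitoring in section 13.2. The documents do not support these readings. At grade 4 both texts point to stopping sorafenib. The bar depends on the counting rule. Nothing in the documents allows an effect on the analysis or the boundaries to be derived.

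**Conclusion.** The point holds in a limited form. The grade 2 non-hematologic cell of Table 2 cannot be followed as printed. The reduction limits conflict at the third single-level step from level 0: three steps under section 5.2, against two reductions in the footnotes and two levels below 0 in the dose-level table. The grade 4 texts differ in force and in the drugs covered, which is an ambiguity and not an opposition. The section 5.3 reference is a numbering error with an identifiable likely target.

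The grade 2 finding assumes that the printed cell matches the source file. The limit finding assumes reductions of one level at a time. Confidence is moderate. The text should be corrected because it concerns patient safety and the correction is cheap. No change to sample size, power, efficacy analysis or stopping boundaries follows.

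**What to change.** Reconcile sections 5.0 and 5.2, the dose-level table, and Tables 2 and 3 so that:

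- the Table 2 grade 2 non-hematologic cell holds one instruction, after a check of the source file for a lost deletion mark;
- there is one reduction limit, which says whether it counts reductions or dose levels, agrees with the ladder and the dose-level table, and has its footnote marker in place;
- the grade 4 non-hematologic rule has one stated force and names the drug or drugs affected;
- the governing table is stated, with any toxicity-specific exceptions in Tables 1 and 3 identified as such;
- the reference to section 5.3 is corrected.

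Which action, dose or limit applies is for the investigators to decide. The cost is a wording amendment, with no added patients, visits or data.

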- Azacitidine 75 mg/m^2 will be administered subcutaneously (SQ) or intravenously (IV) daily for 7 days per cycle. Cycles should be repeated every 4-8 weeks at the discretion of the treating physician. The next azacitidine course may be started before 4 weeks or after 8 weeks if felt to be in the best interest of the patient and only after discussion with the PI.
- Sorafenib will be administered orally at a dose of 400 mg twice daily every day continuously. Sorafenib will only be held for sorafenib-related toxicity.

Both agents will start on the same day of the first cycle. Sorafenib will be given continuously thereafter unless there is a Sorafenib-related toxicity. It will be re-started as soon as that toxicity has resolved to a Grade 1 or baseline status. The first dose of each course of Azacitidine will constitute the beginning of the next cycle of treatment.

Dose reductions for both agents are allowed but should be discussed with the PI and documentation of the justification recorded in the chart.

One cycle of therapy is defined 7 days of azacitidine and continuous dosing of sorafenib. Patients will receive one cycle of therapy every 4 weeks (with a desired dose schedule of 4 week cycles) and can be delayed up to 56 days. If the treating physician feels that one or both of the drugs must be held for a longer period of time, then it must have PI approval.

Subsequent courses of azacitidine will be given if the ANC is equal or greater than $1.0 \times 10^9/L$ (or lower if the treating physician feels in the best interest of the patient and after discussion with PI) and the platelets are equal to or greater than $30 \times 10^9/L$ (unless transfusion dependent), in the absence of residual leukemia in the bone marrow (for the first 3 cycles of therapy, it is intended that the azacitidine cycles are administered every 4 weeks despite cytopenias and even if full recovery to the above levels has not occurred). If prolonged myelosuppression (more than 60 days) with evidence of a hypocellular marrow (marrow cellularity less than 5% without evidence of leukemia) is observed subsequent courses of azacitidine may be given at a lower dose after discussion with the PI. If the peripheral counts do not recover (ANC $< 1 \times 10^9/L$ (or to baseline value) and/or platelets $< 30 \times 10^9/L$ (unless transfusion dependent) but there is evidence of residual leukemia in the bone marrow, subsequent cycles can be administered earlier than 4 weeks at the

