Patients with leukemias and MDS usually present with abnormal peripheral blood counts at the time therapy is started and myelosuppression is an expected event during the course of therapy for acute leukemias and myelodysplastic syndromes. Thus, no dose adjustments or treatment interruptions for myelosuppression will be planned for the first 4 weeks of therapy. After this time, treatment interruptions and dose adjustments may be considered according to the following guidelines:

Patients with neutropenia or thrombocytopenia as a consequence of the disease, do not require treatment interruptions for myelosuppression. Dose-reductions in these patients should be considered in an individual case after discussion with the PI. The following guidelines can be used for these patients:

Patients with a response and pre-cycle counts of neutrophils $> 1 \times 10^9/L$ and platelets $>30 \times 10^9/L$ who have sustained low counts of neutrophils $<0.5 \times 10^9/L$ or a platelet count $<20 \times 10^9/L$ for more than 2 consecutive weeks in the current cycle, may receive a subsequent course. A reduction of up to 2 dose levels may be considered if the myelosuppression was deemed severe and life threatening by the treating physician, and if it is in the patient's best interest after discussion with the PI.

If there are persistent peripheral blood blasts, or the bone marrow shows $>5\%$ blasts, continue treatment regardless of neutrophil and platelet count and give supportive care as needed. After 3 cycles, there should be clear evidence of benefit (reduction in bone marrow blasts, improving counts with reduction in transfusion requirement or other clinical improvement in the opinion of the treating physician) in order to continue treatment regardless of the counts.

If no marrow evidence of leukemia, may hold therapy with azacytidine until recovery of granulocytes to $\geq 1 \times 10^9/L$ and platelets $\geq 30 \times 10^9/L$, then resume at same or 1 lower dose level according to guidelines mentioned above. In general, in the absence of other toxicity, it is recommended that therapy with sorafenib is not interrupted in a responding patient even in the presence of cytopenias (unless discussed with PI).

5.2 Dose escalation:

Dose escalation of sorafenib to 600 mg twice daily will be permitted provided:

- Patient has not experienced any grade 3 or higher non-hematologic toxicity, and

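### For sorafenib, Table 2 and Sections 4.2.1 and 5.1 give conflicting directions on treatment-related cytopenia, and the 28-day footnote does not say which drug it stops

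*Combined protocol and SAP*

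**What the plan says.** Four provisions bear on cytopenia during treatment.

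- **Table 2, hematologic row (Section 5, after 5.2).** The table is titled "Dose Modifications for Sorafenib-Associated Toxicity". Grade 3 and Grade 4 both lead to the dose being withheld until the toxicity falls to Grade 2 or less, then restarted at a lower level. The Grade 4 cell adds an alternative: "or discontinue at the discretion of the principal investigator after discussion with study supporter". Footnote a, marked on the Grade 4 cell only, reads: "If no recovery after 28 day delay, treatment should be discontinued".
- **Section 5.1.** In general, and absent other toxicity, "it is recommended that therapy with sorafenib is not interrupted in a responding patient even in the presence of cytopenias", unless discussed with the principal investigator (PI).
- **Section 4.2.1, cycle timing.** "Cycles should be repeated every 4-8 weeks at the discretion of the treating physician". Later in the same section, a cycle "can be delayed up to 56 days", and a longer hold of either drug or both needs the PI's approval.
- **Section 4.2.1, prolonged myelosuppression.** "If prolonged myelosuppression (more than 60 days) with evidence of a hypocellular marrow" and no leukemia, further azacitidine may be given at a lower dose after discussion with the PI. Sorafenib is not mentioned in that sentence.

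Section 5 also lets the two drugs be adjusted independently and allows variation after discussion with the PI.

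**The concern.** A responding patient whose low counts are attributed to sorafenib falls under Table 2 and Section 5.1 at the same time. One tells the site to withhold the drug. The other advises it not to. If the cytopenia is Grade 4 and does not recover, footnote a ends treatment at 28 days, while Section 4.2.1 contemplates holds of either drug that run past 56 days.

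What is at stake is a hold-and-stop rule that matters for safety. Two sites could handle like patients differently, each with support in the text, so that sorafenib exposure, recorded reasons for stopping and the classification of protocol deviations would depend on which passage was read. The trial-level toxicity boundary in Section 13.2 counts only non-hematologic events of Grade 3 or higher, so it does not act as a check on this.

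**Working it through.** The documents give no figure to reproduce here. The check sets the passages side by side and adds some day arithmetic.

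**1. Withhold or continue sorafenib.** The case is a responding patient with Grade 3 or 4 cytopenia attributed to sorafenib and no other toxicity.

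| Passage | Direction for sorafenib | Exception in the text |
|---|---|---|
| Table 2, Grade 3 | Withhold, resume one level lower | None in the cell |
| Table 2, Grade 4 | Withhold, resume two levels lower, or discontinue | Discontinuing at PI discretion |
| Section 5.1 | Do not interrupt | After discussion with the PI |

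Both sources are phrased as recommendations and neither cites the other, so the text gives no order of precedence. This conflict does not depend on any of the day limits.

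**2. Stop or keep holding sorafenib.** Footnote a sets 28 days without recovery as the end of treatment. Section 4.2.1 allows either drug to be held beyond 56 days with approval. Footnote a has no exception. By contrast, the non-hematologic part of Table 2 has a 60-day limit that is waived for patients deriving clinical benefit, so a reader may take the stricter hematologic wording as deliberate.

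**3. What *treatment* means in footnote a.** Table 1 names sorafenib when it discontinues. The non-hematologic Grade 4 cell of Table 2, and Table 3, refer to protocol therapy. Footnote a does neither.

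- If it means sorafenib only, stopping sorafenib while giving azacitidine is compatible with the more-than-60-day sentence, because the drugs are adjusted independently.
- If it means all protocol therapy, the two conflict. Counting myelosuppression from the start of a 28-day cycle (an assumption), more than 60 days is more than 60 − 28 = 32 days past the next due date. Counting from the due date, it is more than 60 days. Both exceed 28.

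**4. The 56-day figure.** 4 weeks = 4 × 7 = 28 days and 8 weeks = 8 × 7 = 56 days.

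- Read as the interval between cycle starts, the delay is 56 − 28 = 28 days, equal to the footnote limit. There is no conflict.
- Read as the length of the delay itself, it exceeds the limit by 56 − 28 = 28 days.

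The text does not state the starting day, so either reading is open.

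**5. Why the interval reading does not settle sorafenib.** Azacitidine has a due date each cycle. Sorafenib is continuous, so a delay naturally runs from the day it is withheld. As an illustration, if it is withheld on day 10 of a later cycle, 28 days are reached on day 10 + 28 = 38, well inside a 56-day interval.

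**The case against.** The strongest reply has three parts. First, Table 2 is a sorafenib table and marker a sits on the Grade 4 cell alone, so the 28-day limit is narrow. Second, 56 days fits an 8-week cycle and the more-than-60-day sentence is about azacitidine, so the three limits need not collide. Third, flexibility is written in throughout: the tables are recommendations, Section 5.1 is qualified, and variation with the PI is allowed. Section 4.2.1 also holds sorafenib only for sorafenib-related toxicity, and Section 5.1 requires no interruption for disease-related cytopenia, which narrows the overlap further.

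Most of this stands. A reader might infer that hematologic toxicity in general has three contradictory limits (28, 56 and 60 days), so that the same patient is both stopped and continued. The documents do not establish that, for the reasons just given.

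A reader might also infer that patients in CRi are the affected group and that the primary endpoint after three cycles is therefore compromised. That is not supported either. CRi requires only neutrophils below 1.0 or platelets below 100 × 10⁹/L, whereas a further azacitidine course may proceed at neutrophils of at least 1.0 and platelets of at least 30. A CRi patient with adequate neutrophils and platelets of 30 to 99 therefore needs no azacitidine delay. For the first three cycles azacitidine is intended every 4 weeks despite cytopenias, and Section 13.3 keeps every patient who received at least one dose of the combined agents in the efficacy analysis. The CRi share in the earlier trial does not measure how often Grade 4 counts persist.

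What the reply does not remove is the disagreement over sorafenib itself. Discretion permits a departure from a default, but the text does not say whether the default is Table 2 or Section 5.1, nor whether footnote a stops one drug or two.

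**Conclusion.** The point holds for sorafenib. Table 2 and Section 5.1 differ on withholding it in a responder with Grade 3 or 4 treatment-related cytopenia. Footnote a and Section 4.2.1 differ on how long a Grade 4 hold may last. The conflict with the azacitidine sentence is conditional on footnote a meaning all protocol therapy, and the 56-day figure alone proves nothing.

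This rests on two assumptions: that the cytopenia is attributed at least partly to sorafenib, and that the patient is responding where Section 5.1 is invoked. The number of such patients cannot be derived, because the documents give no rate or duration of Grade 3 or 4 cytopenia on this combination. The point does not touch the sample size, the power or the stopping boundaries. It should be corrected because it concerns a safety-relevant rule and is cheap to settle.

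**What to change.** Reconcile the Table 2 hematologic row and footnote a with Sections 4.2.1 and 5.1. The amended text should state:

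- for each drug separately, which passage governs treatment-related cytopenia, including in a responding patient;
- which drug or drugs *treatment* refers to in footnote a;
- from which day the 28-day, 56-day and more-than-60-day periods are each counted, and whether 56 days is a cycle interval or a delay;
- whether the PI approval for longer holds in Section 4.2.1 overrides footnote a.

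Cross-references between the three places would keep them aligned. The content of the rule is for the clinical team to decide, and no view is taken here on which passage is right. The cost is a short clarifying amendment to one table row, one footnote and a few sentences, with no change to the sample size or analysis.
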